9.11. Definition of End of Study

The end of study is the point at which all the study data has been entered and queries resolved.

10. SAFETY REPORTING

The safety reporting window will start from the time of consent to the point that the participant completes the study. The investigator will follow up SAEs until event resolution or stabilisation for related events only.

10.1. Definition of Serious Adverse Events

A serious adverse event is any untoward medical occurrence that:

- results in death
- is life-threatening
- requires inpatient hospitalisation or prolongation of existing hospitalisation
- results in persistent or significant disability/incapacity
- Consists of a congenital anomaly or birth defect.

Other 'important medical events' may also be considered a serious adverse event when, based upon appropriate medical judgement, the event may jeopardise the participant and may require medical or surgical intervention to prevent one of the outcomes listed above.

NOTE: The term "life-threatening" in the definition of "serious" refers to an event in which the participant was at risk of death at the time of the event; it does not refer to an event which hypothetically might have caused death if it were more severe.

10.2. Reporting Procedures for Serious Adverse Events

A serious adverse event (SAE) occurring to a participant should be reported to the REC that gave a favourable opinion of the study where in the opinion of the Chief Investigator the event was 'related' (resulted from administration of any of the research procedures) and 'unexpected' in relation to those procedures. Reports of related and unexpected SAEs should be submitted within 15 working days of the Chief Investigator becoming aware of the event, using the HRA report of serious adverse event form (see HRA website).

11. STATISTICS AND ANALYSIS

11.1. Statistical Analysis Plan (SAP)

The plan for the statistical analysis of the study is outlined below. There is not a separate SAP document in use for the trial.

11.2. Description of the Statistical Methods

This is a feasibility pilot RCT, therefore the aim of this study is not to provide a measure of efficacy but to determine whether it is possible to run a large scale RCT. Participant demographics will be summarised using standard descriptive statistics. The following components will also be analysed:

- The mean and SD of the primary outcome measure the BBS will be analysed to provide a sample size calculation for a larger RCT
- Recruitment – The number of recruited participants in the recruitment window, the number of participants screened to allow for the recruitment target to be met and the reason for non-entry into the trial which will provide realistic expectations of recruitment for a future larger scale RCT.
- Randomisation – Is randomisation acceptable to participants in this study? Does randomisation create comparable groups?
- Intervention acceptability – Is the intervention acceptable to participants? Do any participants fail to complete the intervention? Adherence to the prescribed BW programme will be measured through a collection of a diary. These issues will also be explored in more depth as part of the qualitative study.
- Retention of participants – Drop outs and wherever possible the reason for drop out will be recorded.
- Fidelity - Fidelity checks will be conducted, this will involve observing treatment sessions to check adherence to the protocol.

Qualitative interviews:

The data from the interviews will be analysed using thematic analysis, using six steps proposed by Braun and Clarke transcribing the data, generating initial codes, searching for themes, reviewing themes, defining and naming themes and producing the report. Data will be transcribed from the audio recordings, whilst initial ideas are recorded. Then data will then be coded, before codes are grouped into themes. To aid the process of data analysis NVIVO 10 (or later version) software will be used, this computer programme is designed for the analysis of qualitative data. It allows the collection, sorting and analysing of data from qualitative methods such as interviews.

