6. OBJECTIVES AND OUTCOME MEASURES

Objectives	Outcome Measures	Timepoint(s) of evaluation of this outcome measure (if applicable)

Primary Objective To test the procedures and processes of the trial and to estimate parameters for the main trial sample size calculation
	
 • Berg Balance Scale (BBS) (to calculate sample size) – Static and dynamic balance activities of varying difficulty are performed to provide a measure of falls risk and balance • Participant recruitment figures • Participant retention figures • Randomisation acceptability • Number of protocol violations from fidelity checks • BW programme diary to provide a measure of adherence • Participant safety through recording any falls and injuries whilst completing the BW programme • Qualitative interviews to determine acceptability of intervention and delivery with participants and physiotherapists 	Baseline and 3 months

Secondary Objectives To examine the consistency of the effects of the backwards walking programme on falls risk, balance, strength and gait speed following hip and knee joint arthroplasty
	
 • Four Square Step Test (FSST)- a test of dynamic balance that clinically assesses a person's ability to step over objects forward, sideways, and backwards • 2 minute walk test (2MWT)- assesses walking distance • 30 second chair rise test - assesses sit to stand ability and provides a measure of lower limb strength and dynamic balance. • Activities-specific Balance confidence scale (ABC) - self-reported measure of confidence in performing various ambulatory activities without falling • Falls diary - records the frequency of falls 	Baseline and 3 months

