9.8. Subsequent Visits

As this is a feasibility pilot study the main aims are not to assess the effectiveness of the intervention but to trial the acceptability and feasibility of the study protocol and pilot its delivery at the Nuffield Orthopaedic Centre in Oxford. For this reason the main assessments for the study relate to recruitment, retention and acceptability. The research clinician will therefore collect data throughout the trial on the number of patients screened, the number that consented, the reason for not consenting, the number of drop outs, the availability of the outcome measure data and the standard deviation of the BBS in order to estimate the sample size. The acceptability of the intervention will be measured through collection of the BW programme diary which will provide a measure of adherence. Participants will also be invited to take part in an interview to determine the study acceptability.

Fidelity checks

Fidelity checks will be made by a member of the study team who is not blinded to treatment allocation to ensure adherence to the study protocol from the recruiting and treating clinicians. These will take place mid-way through study recruitment once approximately 20 participants have been randomised.

12 week follow up

Participants will be followed up at 12 weeks for the final assessment. Participants will be asked to return to the physiotherapy clinic or where possible this appointment will tie in with their final physiotherapy appointment at 12 weeks. The outcome measure assessments will be the same as at baseline and the research clinician will ensure they collect in the falls diary and if applicable BW programme diary.

Qualitative interviews

Patients taking part in the study, and treating clinicians, will be invited to take part at the in a semi-structured interview to determine if the study procedures and trial design were acceptable to participants. This will take place after the participants have completed their 12 week follow up and physiotherapists have completed the intervention delivery.

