11.3. Sample Size Determination

The sample size for the feasibility randomised controlled trial will be 40 participants, allowing for 20 participants per group. Whitehead et al²⁴ suggests that feasibility trials recruit 20 participants per group for an 80% powered main trial, assuming a small effect size of 0.1 to 0.3.

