12.3. Data Recording and Record Keeping

All trial data will be entered onto paper CRFs, then entered onto Microsoft Excel 2010 or newer or SPSS computer software (SPSS version 26.0 or newer) using password protected files on password protected OUH FT computers. Any study documents and data, such as the signed consent form will be stored in a lockable secure room in the Physiotherapy Research Unit at the Nuffield Orthopaedic Centre. The participants will be identified by a unique study specific participant number in any database. The name and any other identifying detail will NOT be included in any trial data electronic file. Qualitative transcripts will use pseudo initials and all identifiable information regarding people or place will be removed from transcripts. Personal data will be kept for 1 year after the study has finished and the study data will be stored on the OUH FT server for 5 years.

For participants who agree in their Informed Consent to be contacted for future research, the consent form will be retained as the basis for retention of details and future approach. Those contact details will be held securely, separately from the research data, and kept updated. They will be held for an indeterminate period of time.

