
22. Appendix 1

Scale Instructions

While exercising we want you to rate your perception of exertion, i.e., how heavy and strenuous the exercise feels to you. The perception of exertion depends mainly on the strain and fatigue in your muscles and on your feeling of breathlessness or aches in the chest.

Look at this rating scale; we want you to use this scale from 6 to 20, where 6 means "no exertion at all" and 20 means "maximal exertion."

- 6 No exertion at all
- 7
- 8 Extremely light
- 9 Very light
- 10
- 11 Light
- 12
- 13 Somewhat hard
- 14
- 15 Hard (heavy)
- 16
- 17 Very hard
- 18
- 19 Extremely hard
- 20 Maximal exertion

Borg RPE scale
© Gunnar Borg, 1970, 1985, 1994, 1998

Figure 7.1 The Borg RPE scale for perceived exertion.

- 9 corresponds to "very light" exercise. For a normal, healthy person it is like walking slowly at his or her own pace for some minutes.
- 13 on the scale is "somewhat hard" exercise, but it still feels OK to continue.
- 17 "very hard" is very strenuous. A healthy person can still go on, but he or she really has to push him- or herself. It feels very heavy, and the person is very tired.
- 19 on the scale is an extremely strenuous exercise level. For most people this is the most strenuous exercise they have ever experienced.

Try to appraise your feeling of exertion as honestly as possible, without thinking about what the actual physical load is. Don't underestimate it, but don't overestimate it either. It's your own feeling of effort and exertion that's important, not how it compares to other people's. What other people think is not important either. Look at the scale and the expressions and then give a number.

Any questions?

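### The plan does not say which Berg Balance Scale (BBS) SD feeds the main-trial sample size, and plans no interval, baseline to 12-week correlation or baseline-adjusted SD, although paired values are collected

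*Combined protocol and SAP*

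**What the plan says.** Section 6 makes it part of the primary objective "to estimate parameters for the main trial sample size calculation". The outcome listed there for that purpose is the "Berg Balance Scale (BBS) (to calculate sample size"), with baseline and 3 months as its time points.

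Section 11.1 states: "There is not a separate SAP document in use for the trial". Sections 11.2 and 11.3, with the remarks in section 9.8, are therefore all there is.

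- Section 11.2, first bullet: "The mean and SD of the primary outcome measure the BBS will be analysed to provide a sample size calculation for a larger RCT".
- Section 9.8, among the data to be collected: "the standard deviation of the BBS in order to estimate the sample size".
- Section 11.3 sets 20 participants per group from a cited rule for an 80% powered main trial, "assuming a small effect size of 0.1 to 0.3".

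Section 9.8 says the 12-week assessments repeat those at baseline, so each completer will have a pair of BBS values. Section 9.4 stratifies randomisation by arthroplasty type. Section 9.10 says that randomised participants who withdraw are not replaced.

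**The concern.** With two visits and two arms there are several candidate SDs: baseline, 12-week or change, each taken in one arm, pooled within arm or across the whole sample. They can lead to different sample sizes, and the plan does not choose among them. It also plans nothing that shows how precise the chosen SD is, or how much of the 12-week variance the baseline score explains.

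The pilot exists partly to deliver this input. If it reports a sample size from a bare SD, two things are left out: the uncertainty in that figure, which is wide with at most 40 participants, and the saving that a baseline-adjusted main trial could make from data the pilot already holds.

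**Working it through.** **Inputs from the documents.** 40 participants, 20 per group; 80% power; standardised effects of 0.1 to 0.3 (section 11.3). BBS at baseline and 12 weeks (sections 6 and 9.8), with a maximum of 56 (section 9.7).

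**Assumptions, not in the documents.** Two-sided 5% test. Main trial sized on a fixed difference in BBS points equal to 0.3 of the estimated 12-week SD (the top of the section 11.3 range). Baseline to 12-week correlation (rho) of 0.3, 0.5 or 0.7. Completers: 40, or 32 if 20% are lost.

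**1. The plan's own figure.** 2 × 20 = 40 reproduces. The 20 is a cited rule, so it cannot be derived from the stated inputs alone. The title of the cited paper gives the aim "to minimise the overall trial sample size for the external pilot and main trial". As a check, I minimised pilot plus main-trial total over the pilot size, using a non-central t allowance for the estimated variance. The optimum per group is 38, 20 and 14 at effects of 0.1, 0.2 and 0.3. So 20 is compatible with the stated range.

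**2. Main-trial size from the point SD.** n per arm = 2(1.960 + 0.842)² / 0.3² = 174.4, so 175 per arm and 350 in total.

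**3. Precision of that figure.** The 95% limits for a pooled within-arm SD are the estimate times √(df/χ²₀.₉₇₅) and √(df/χ²₀.₀₂₅), with df = n − 2.
- 38 df: √(38/56.90) = 0.817 and √(38/22.88) = 1.289. For a fixed difference in points, the sample size scales with the square: 0.668 and 1.661. Per arm, 174.4 × 0.668 = 116.5 and 174.4 × 1.661 = 289.7, so 234 to 580 in total (scaling the rounded 350 gives 581).
- 30 df (32 completers): SD factors 0.799 and 1.337, total 224 to 624.

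**4. What baseline adjustment changes.** Residual variance is (1 − rho²) times the raw variance; any further gain from arthroplasty type is ignored.
- rho 0.3: 174.4 × 0.91 = 158.7, total 318.
- rho 0.5: 174.4 × 0.75 = 130.8, total 262.
- rho 0.7: 174.4 × 0.51 = 89.0, total 178.

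The residual SD has n − 4 = 36 df with 40 completers. At rho 0.5, the 262 then has a range of 174 to 442. For comparison, a change-score SD (equal SDs at both visits, variance factor 2(1 − rho)) gives 490, 350 and 210, so the label on the SD matters.

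**5. Consequence for power.** Suppose the point SD is used as it stands, for the same analysis it came from. Average power is E[Φ(2.802·√(χ²_df/df) − 1.960)] = 78.3% at 38 df and 77.9% at 30 df. Power falls below 80% whenever the estimate falls below the true SD, which has probability 53% at either df. It falls below 70% with probability 18% (38 df) or 21% (30 df). At 38 df, a non-central t allowance restores average power to 80% for 4.5% more participants (366 against 350).

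**6. Raw SD used for an adjusted main trial.** This errs towards too many participants. The chance of power below 80% is P(χ²₃₈ < 38(1 − rho²)) = 37%, 13% and 0.5% at rho 0.3, 0.5 and 0.7.

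**The case against.** The case for leaving the text alone has real force.

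- **The interval can be worked out by a reader.** It depends only on the SD and its degrees of freedom, and section 9.8 already records drop-outs and availability of outcome data. This stands if the reported SD is labelled. It does not help with the correlation or the residual SD, which cannot be recovered from a published mean and SD.
- **Section 6 names both time points.** The natural reading is that the BBS will be summarised at each visit, so a report of one unlabelled SD is the worst case. The plan also does not exclude an interval; it plans none. Both stand. It still does not say which SD sets the sample size.
- **The SD may cancel.** Section 11.3 speaks only of standardised effects. A main trial sized on one would need 350 at 0.3 whatever the SD. This stands, and the range in step 3 depends on a fixed difference in BBS points. But the plan says that the SD will be used to calculate the sample size, and that is meaningful only for a difference in points.
- **Adjustment is a choice for the main trial.** True. No passage commits to it, and the correlation will be imprecise. Reporting it keeps that choice open and informed.

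A reader might also infer that 40 is too few. Step 1 does not support that. Nor is the information lost: section 12.3 says "the study data will be stored on the OUH FT server for 5 years", so every quantity could be computed when the main trial is designed.

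**Conclusion.** The point holds as a cheap improvement of low to moderate severity. The plan leaves the SD unnamed and plans neither an interval nor any use of the paired baseline values, on a quantity that belongs to its primary objective.

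On the stated assumptions, a point total of 350 carries a 95% range of about 234 to 580 with 40 completers, and baseline adjustment would move it to 318, 262 or 178 at rho 0.3, 0.5 or 0.7. These figures rest on a two-sided 5% test, a fixed difference in points and assumed correlations. The chi-square limits also assume roughly normal scores, which the cap of 56 may strain.

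It would be tempting to read the 53% chance of power below 80% as a seriously underpowered main trial. That is not supported: nearly any unbiased variance estimate gives about an even chance, and the average shortfall is under 2 percentage points. Using the raw SD for an adjusted analysis is conservative on average.

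**What to change.** Replace the first bullet of section 11.2 with:

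> In randomised participants with 12-week BBS, we will report the 12-week SD pooled within arm, the residual SD from a regression of 12-week BBS on arm, baseline BBS and arthroplasty type, and the within-arm baseline to 12-week correlation, each with a 95% CI. The main-trial sample size will be shown for a stated difference in BBS points at the point estimate and at the confidence limits of the pooled and residual SD.

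Name the same SDs in section 9.8. No separate inflation factor is needed here: the sample size across the interval already shows the uncertainty, and any inflation belongs in the main-trial protocol. Reporting how many participants score 56 at each visit is optional.

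The cost is one regression on data already planned and a few lines of text, with no new visits or participants. The downsides are an imprecise correlation (for r = 0.6, a 95% CI of about 0.35 to 0.77 with 40 completers) and intervals that are approximate because the BBS is capped.

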9.4. Randomisation

Participants will be randomised once informed consent has been gained. A randomisation list will be generated using the web-based randomisation system Sealed Envelope¹⁷ by an independent researcher

at the study site who is not part of the study team. Randomisation will be stratified by arthroplasty type. Permuted block randomisation will be used to ensure the strata are balanced between the groups. The independent researcher will then follow the sequence list generated to write each individual allocation in an opaque sealed envelope which will be labelled on the outside in number order from 1-20 with each stratum beside it (knee or hip arthroplasty). When a participant has completed the baseline study assessment a second independent researcher will take the opaque sealed envelope in number sequence, based on the participant's type of arthroplasty, to determine that participant's treatment allocation. This treatment allocation will then be passed onto the treating physiotherapist via a referral form and the participant will be informed of their group allocation when they attend their physiotherapy sessions. The second independent researcher will also complete a randomisation log to document each participant's allocation.

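### With 20 per arm, baseline similarity says little about whether the allocation procedure worked; section 11.2 should check the allocation records instead

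*Combined protocol and SAP*

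**What the plan says.** The primary objective in section 6 is "To test the procedures and processes of the trial and to estimate parameters for the main trial sample size calculation". Section 11.2 states that "the aim of this study is not to provide a measure of efficacy but to determine whether it is possible to run a large scale" trial, then lists the components to be analysed. Under randomisation it puts two questions: whether participants accept it, and "Does randomisation create comparable groups". Only the second is at issue here. The section names no variables for that comparison, no measure of difference and no limit. Its stated method for baseline data is descriptive: "Participant demographics will be summarised using standard descriptive statistics". Section 11.1 says there is no separate SAP, so these details are not given elsewhere.

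Sections 7 and 9.4 describe permuted blocks stratified by hip or knee. An independent researcher generates the list and fills opaque envelopes numbered within stratum. A second independent researcher opens them in order after the baseline assessment and "will also complete a randomisation log". Section 11.3 sets the size at 40, "allowing for 20 participants per group".

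**The concern.** Randomisation makes groups comparable in expectation. It does not promise that a single sample of 40 will look alike on every variable left to chance. Here that means age, weight, falls history, the four physical tests and the balance confidence scale, among others. A sound procedure will often leave visible differences on some of these, and a procedure that was not followed can still produce similar groups.

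Testing trial processes is the pilot's primary purpose, and allocation is one of those processes. If the comparability question is answered from the baseline table, a chance imbalance could be read as a fault in the method, or a tidy table as proof that envelopes were used properly. Meanwhile the direct evidence that section 9.4 generates has no planned analysis.

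**Working it through.** **Inputs from the documents.** 20 per arm (section 11.3; 2 × 20 = 40 reproduces the stated total). One stratification factor, joint type (sections 7 and 9.4). Five baseline outcome measures: four physical tests and one questionnaire (section 9.7). Falls figures of 28% and up to 40% (section 5), used only to illustrate a binary variable.

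**Assumptions, not in the documents.** Cut-offs of 0.25 and 0.5 SD; five or ten variables; a common correlation between 0 and 0.8.

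**One continuous variable, correct randomisation.** The standardised mean difference has standard error √(2/20) = 0.316, and P(|difference| > t) = 2 × [1 − Φ(t/0.316)].
- t = 0.25: 0.25/0.316 = 0.79, probability 0.429.
- t = 0.5: 0.5/0.316 = 1.58, probability 0.114.
- t = 1: 1/0.316 = 3.16, probability 0.002.

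**At least one of k variables beyond 0.5 SD.** If independent, 1 − (1 − 0.114)^k. Correlated cases use the same normal model with a common correlation.

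| Correlation | k = 5 | k = 10 |
|---|---|---|
| 0 | 45% | 70% |
| 0.5 | 37% | 54% |
| 0.7 | 30% | 41% |
| 0.8 | 26% | 34% |

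Estimating the SDs from the data, as would happen in practice, raises these slightly: for ten variables, simulation gives 73% at correlation 0 and 44% at 0.7.

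**One binary variable, exact binomial, 20 v 20.** At 28% and 40% prevalence the arms differ by 15 percentage points or more in 38% and 42% of trials, and by 20 points or more in 22% and 26%.

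**Can the comparison detect a real fault?** Suppose faulty allocation shifts one variable by a true 0.5 SD. The observed difference then exceeds 0.5 SD in 50% of trials, against 11% under sound allocation. A two-sided 5% test (none is planned) would have 35% power. So the comparison carries some information about a single variable named in advance, but it misses such a fault about half the time.

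**What the design fixes.** Arm totals and the hip/knee split follow from the list, apart from incomplete blocks. Comparing these counts with the list is a real check that the sequence was followed.

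**What other sections check.** Section 6 counts protocol violations from fidelity checks. Section 9.8 applies those checks to recruiting and treating clinicians, at about 20 randomised. Section 11.2 describes them as observing treatment sessions. Section 14 requires deviations to be documented. None specifies checking envelope order or matching the log to the list.

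**The case against.** The strongest reply is that section 11.2 only poses a question. It sets no threshold, test, pass/fail rule or progression criterion, and baseline data are to be described. On that reading the plan is already close to a plain baseline table. This stands: a reader might infer that the plan will pass or fail the randomisation on baseline balance, or will run baseline significance tests, and the documents support neither.

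A reader might also infer that the comparison says nothing at all about the procedure. That goes too far. Joint type and arm counts are constrained by the blocks, so departures from them are informative. A difference above 1 SD on one variable arises by chance in only about 0.2% of sound trials.

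Nor is process evidence ignored altogether. An envelope used out of order would be a recordable deviation under section 14 if somebody noticed it, and randomisation acceptability is a listed measure in section 6. But these provisions depend on the error coming to light; no planned step looks for it.

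Finally, the multi-variable percentages depend on assumed counts, correlations and a cut-off that the plan does not use. The five outcome measures all concern balance, mobility, strength or balance confidence, so correlation is plausible and the lower part of the range deserves weight.

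**Conclusion.** The point holds as a minor one. At 20 v 20, observed baseline similarity is a poor answer to whether the allocation procedure worked, beyond joint type, arm size and very large differences. The single-variable figures (43% beyond 0.25 SD, 11% beyond 0.5 SD) rest only on 20 per arm, correct 1:1 allocation, an unstratified variable and a normal approximation. The ranges of 26–45% for five variables and 34–70% for ten rest on the further assumptions listed above.

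Because the plan attaches no decision rule to the question, what is at risk is the interpretation and reporting of one feasibility component. There is no efficacy analysis to affect, and the estimation of the Berg Balance Scale SD and the recruitment and retention counts are untouched.

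**What to change.** In section 11.2, keep the question on acceptability and replace the one on comparability with a process check. Of all randomisations, report n/N in which the next envelope in sequence was used, from the correct stratum, after the baseline assessment was complete, with the log agreeing with the generated list. Describe each discrepancy. Report stratum and arm counts against the list. Present baseline characteristics by arm descriptively, with no verdict on comparability; stating that no baseline significance tests will be done is a safeguard, since none is planned.

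The list, the envelopes and the log already exist under section 9.4. The documents do not say whether the log holds the envelope number and the date of opening; if it does not, add those two columns. The cost is a change of wording and one reconciliation of up to 40 rows, with no extra participants or visits.
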